#### Treatment administration period:

Treatments (BI 1026706 or placebo) will be administered twice daily starting after randomization at Day 1 in the clinic (Visit 2) and lasts until Day 28. The last study drug administration will be performed in the evening of Day 28 at home.

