#### Further endpoints related to safety assessment:

- Number (%) of subjects with treatment emergent adverse events (TEAE).
- Number (%) of subjects with drug related AEs

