#### 7.3.4 Safety analyses

Safety will be assessed for the further endpoints listed in [Section 5.1.3](#) as well as the further safety assessments described in [Section 5.3](#). All treated subjects (that is, all subjects who received at least one dose of study drug), will be included in the safety evaluation. Safety analyses will be descriptive in nature and will be based on BI guideline ‘Analysis and presentation of adverse event data from clinical trials’ (001-MCG-156).

The analyses will be done by ‘treatment at onset’.

Tabulations of frequencies/proportions will be used for the evaluation of categorical (qualitative) data, and tabulations of descriptive statistics will be used to analyze continuous (quantitative) data.

Measurements (such as ECG, vital signs, or laboratory parameters) or AEs will be assigned to treatments (see [Section 4.1](#)) based on the actual treatment at the planned time of the measurement or on the recorded time of AE onset (concept of treatment emergent AEs).

[figure not shown]
Therefore, measurements planned or AEs recorded prior to first intake of trial medication will be assigned to 'screening', those between first trial medication intake until the end of the REP will be assigned to ‘on-treatment’, and those between end of REP and end-of-trial examination will be assigned to ‘post-treatment’ and those after the end of trial examination will be assigned to ‘post-study’. These assignments including the corresponding time intervals will be defined in detail in the TSAP.

Additionally, further treatment intervals (analysing treatments) may be defined in order to provide summary statistics for time intervals, such as combined treatments, on-treatment totals or periods without treatment effects (such as screening and post-study intervals).

[figure not shown]
Adverse events will be coded using the MedDRA. Frequency, intensity and causal relationship of AEs will be tabulated by treatment, primary system organ class and preferred term. SAEs and other significant AEs (according to ICH E3), and AESIs will be listed separately (see [Section 5.3.7](#)).

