6. GENERAL ANALYSIS DEFINITIONS

6.1 TREATMENTS

For basic study information on treatments to be administered, assignment of dose groups, and selection of doses, cf. Section 4 of the CTP.

Subjects will be treated with either

- 100 mg BI 1026706 (test treatment, T) or
- placebo (reference treatment, R),

twice daily for 28 +/- 2 days.

The following separate study analysis phases will be defined for the analyses of AEs, laboratory tests, vital signs and body weight:

- **Screening** (ranging from 0:00 h on day of informed consent until first administration of study drug)
- **On treatment** (separately for each treatment, ranging from the time of first study drug administration [REDACTED] 4 days after the last administration of study drug; note that 4 days after the last trial medication application are defined in CTP Section 5.3.7 as the residual effect period [REP])
- **Post-treatment** (separately for each treatment, ranging [REDACTED] days after the last administration of study drug, i.e. the end of the REP, to start of post-study phase)
- **Post-study** ([REDACTED] after the last administration of study drug or at 0:00 h on the day after the EOT visit, whichever is later)

Note that the post-treatment phase might not exist for individual subjects, e.g. if the EOT visit is [REDACTED] of the last administration of study drug.

Table 6.1: 1 Flow chart of study analysis phases for adverse events, laboratory tests, vital signs and body weight

Study analysis phase	Start	End
Screening	Date of informed consent	Date/time of first administration of study drug
On treatment	Date/time of first administration of study drug	Date/time of last administration of study drug + REP, [REDACTED] * 24 h
Post-treatment ¹	Date/time of last administration of study drug + REP ([REDACTED] * 24 h)	12:00 AM on day after trial completion date
Post study	Date/time of last administration of study drug + REP ([REDACTED] * 24 h) or 12:00 AM on day after trial completion date (whichever is later)	Not defined – a placeholder date is used, e.g. a date after database lock

¹ does not necessarily exist

Displays of AEs, laboratory tests, vital signs and body weight will be presented separately for the treatments, labelled "**BI 1026706**" and "**Placebo**".

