CTR Section 15, Appendix 16.1.9.2.8.2 and Appendix 16.1.9.2.8.3 AE displays will present results for these study treatments during on-treatment phases only, labelled as indicated above. Screening, post-treatment and post-study periods will not be included in this analysis.

CTR Appendix 16.1.9.2.8.1 displays will present results for the following study analysis phases:

- Screening
- On-treatment (separately per study treatment listed above, labelled with the name of the respective study treatment)
- Post-treatment (separately per study treatment listed above, labelled "**Post-BI**" and "**Post-Placebo**")
- Post-study

In CTR Section 15 AE tables and CTR Appendix 16.1.9.2.8.1 displays, a total over both on-treatment phases (i.e., BI 1026706 plus placebo, labelled "**Total on-trt**") will be provided in addition.

In CTR Appendix 16.1.9.2.8.1 displays, a total over all study phases (labelled "**Total**") will be provided in addition.

No total columns will be provided in CTR Appendices 16.1.9.2.8.2 and 16.1.9.2.8.3.

Displays of laboratory tests, vital signs and body weight will present results by study treatment.

More details on the technical implementation of these analyses are provided in the analysis data set (ADS) Plan of this TSAP.

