The frequency of subjects with AEs will be summarised by treatment, primary system organ class and preferred term. This summary table will be shown based on all reported AEs. Furthermore separate tables will be presented for the frequency of subjects with procedural on-treatment AEs, the frequency of subjects with LPS related on-treatment AEs, and the frequency of subjects with non-procedural and non-LPS-related on-treatment AEs. AEs which were considered by the investigator to be related to the investigational study drug will be summarised separately. Separate tables will be provided for subjects with SAEs, subjects with AESIs and subjects with other significant AEs (according to ICH E3 (9)). AEs will also be summarised by maximum intensity.

The system organ classes will be sorted according to the standard sort order specified by the European Medicines Agency (EMA), preferred terms will be sorted by total frequency (within system organ class). The MedDRA version number will be displayed as a footnote in the respective output.

In addition, frequencies of subjects with non-serious AEs that had an incidence of > 5% (in preferred terms) for at least one treatment will be summarised by treatment, primary system organ class and preferred term.

For disclosure of AE data in the European Union Drug Regulating Authorities Clinical Trials (EudraCT) register, additional information not included in a standard AE analysis will be performed. The following three entries will be created:

- AEs per arm for disclosure on EudraCT
- Non-serious AEs for disclosure on EudraCT
- Serious AEs for disclosure on EudraCT

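### The LPS-related and procedural AE tables close 4 days after the last tablet, not by time since the challenge, and AE onset time relative to the challenge is not used

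*SAP*

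**What the plan says.** SAP 6.1 sets four phases: screening, on treatment, post-treatment and post-study. On treatment starts at "Date/time of first administration of study drug" and ends with the residual effect period: "note that 4 days after the last trial medication application are defined in CTP Section 5.3.7 as the residual effect period". Study drug here means BI 1026706 or placebo tablets. No phase starts at the LPS instillation or at either bronchoscopy, although Protocol 1.2 refers to LPS as an IMP and every subject is due to receive it at Visit 6.

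SAP 7.8.1 plans separate tables for "the frequency of subjects with procedural on-treatment AEs, the frequency of subjects with LPS related on-treatment AEs", and a third for on-treatment AEs that are neither procedural nor LPS-related. AEs related to the study drug are summarised separately. For the CTR Section 15 AE displays and two of the appendices, SAP 6.1 adds: "Screening, post-treatment and post-study periods will not be included in this analysis". Appendix 16.1.9.2.8.1 does show all phases, with post-treatment AEs split by arm.

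On timing, Protocol 4.1 states: "The last study drug administration will be performed in the evening of Day 28 at home". Protocol 3.1 places Visit 8 on Day 32 to 34, and Protocol 6.1.2 allows Visit 6 from Day 26 to Day 30. Protocol 5.3.7 collects all AEs until the individual end of trial. Protocol 7.3.4 foresees that "further treatment intervals (analysing treatments) may be defined".

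**The concern.** The residual effect period says how long the tablet may still act. It says nothing about how long a reaction to endotoxin or to two bronchoscopies may take to appear. Protocol 2.3.1 names lung infection and pneumonia as bronchoscopy risks, and such events need not start within a few days. If they start after the tablet window closes, the two tables meant to describe the challenge miss them, although the data are collected.

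The second issue is how challenge reactions are separated from AEs on drug alone. The plan uses only the investigator's classification (LPS-related, procedural, or neither). Fever, headache and nausea are listed LPS effects and are non-specific, so this is a judgement. Onset time is objective: an AE that starts before the Visit 6 bronchoscopy cannot be due to the LPS given there. No planned table in the visible text uses it.

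**Working it through.** The plan gives no figure for the follow-up covered by these tables, so there is none to reproduce. The check is clock arithmetic.

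**Inputs.** Residual effect period 4 days = 96 h (SAP 6.1). Visit 6 on Day 26 to 30 (Protocol 6.1.2). Visit 8 on Day 32 to 34, held fixed when Visit 6 moves, because Protocol 6.1.2 ties later visits to the original schedule. Assumed: last tablet at 22:00 on the Visit 6 day (Protocol 6.2.4 asks for close to 10 p.m.; Protocol 3.1.1 calls Visit 6 the last day of treatment) and Visit 8 at 10:00.

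**Formula.** The window closes at 22:00 on day (Visit 6 + 4). Hours before Visit 8 outside it = max(0, 24 × (Visit 8 day − Visit 6 day − 4) − 12).

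| Visit 6 | Window closes | Visit 8 Day 32 | Day 33 | Day 34 |
|---|---|---|---|---|
| Day 26 | 22:00 Day 30 | 36 h | 60 h | 84 h |
| Day 27 | 22:00 Day 31 | 12 h | 36 h | 60 h |
| Day 28 | 22:00 Day 32 | 0 h | 12 h | 36 h |
| Day 29 | 22:00 Day 33 | 0 h | 0 h | 12 h |
| Day 30 | 22:00 Day 34 | 0 h | 0 h | 0 h |

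**As a share of follow-up.** Assume LPS at 10:30 and Visit 6 on Day 28. From LPS to Visit 8 is 95.5, 119.5 or 143.5 h, so the excluded share is 0/95.5 = 0%, 12/119.5 = 10% or 36/143.5 = 25%. Counted from the second bronchoscopy 24 h later it is 0/71.5 = 0%, 12/95.5 = 13% or 36/119.5 = 30%. With Visit 6 on Day 26 it is 36/143.5 = 25%, 60/167.5 = 36% or 84/191.5 = 44% from LPS. These are shares of hours, not of events.

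**Sensitivity.** If the Day 28 evening tablet is missed and the last one is at 08:00, the window closes 14 h earlier and the Day 28 row becomes 2, 26 and 50 h.

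**Attribution and onset time.** Take the first tablet at 08:00 on Day 1, LPS at 10:00 on Day 28 and the window closing at 22:00 on Day 32. The on-treatment phase is then 758 h: 650 h before LPS (86%) and 108 h after (14%). If a share q of each arm has a challenge AE, independently of other AEs, the risk of any AE is 1 − (1 − a)(1 − q), and an arm difference a − b appears in the all-cause table as (a − b)(1 − q). With assumed a = 30% and b = 15%, the 15 points become 10.5, 7.5 or 4.5 at q = 0.3, 0.5 or 0.7. In the table without LPS and procedural AEs the full 15 points remain if attribution is correct. The documents give no values for a, b or q; the example shows only that recovering the contrast depends on attribution.

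**The case against.** There is a good deal to say on the other side, and most of it stands.

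- A reader might infer that late challenge reactions are lost from the report. They are not. Appendix 16.1.9.2.8.1 shows them by phase and arm, with a total over all phases, and individual data are listed.
- A reader might infer that the TEAE endpoint is too diluted to use. The third table in SAP 7.8.1 answers most of that, and there is a drug-related table besides. Both arms receive LPS, so pooling favours neither arm.
- A reader might infer that a drug effect which amplifies the LPS reaction is hidden once it is called LPS-related. AE displays are by arm, so it would show as an arm difference in the LPS-related table and stay in the all-AE table. It leaves only the third table.
- A reader might infer that anything first found at Visit 8 is excluded. Protocol 7.3.4 assigns AEs by recorded onset, so an AE reported at Visit 8 with an earlier onset can still be on treatment.
- The window follows the protocol's own TEAE definition, and safety is descriptive only. Parts of SAP 6.1 are redacted, and the company AE guideline and analysis data set plan are not visible.

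What this does not answer is narrow: both challenge tables are expressly limited to on-treatment AEs, so an LPS-related or procedural AE that starts after the tablet window cannot enter them.

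**Conclusion.** The point holds as a limited flaw in table definition. On the assumed clock times, the LPS-related and procedural tables omit AEs starting in the last 0 to 36 h before Visit 8 when Visit 6 is on Day 28, 36 to 84 h when it is on Day 26, and none when it is on Day 30. How many events fall there is unknown; the documents give no rates, and a constant hazard should not be assumed. The same AEs remain visible elsewhere in the report, but not in the tables that describe the challenge. The lack of an onset-based split is a smaller, separate gap: the planned attribution tables are useful but rest on judgement, and an objective check is available from data already collected. Neither part affects the primary analysis or invalidates the TEAE endpoint.

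**What to change.** 1. In SAP 7.8.1, remove the on-treatment limit from the LPS-related and procedural tables and count these AEs by arm through the individual end of trial. Keep procedural AEs that start before Visit 6, such as those from blood sampling. Add the matching exception in SAP 6.1, where the Section 15 AE displays are confined to on-treatment phases.
2. Add one all-cause AE table by arm for onset from the first tablet to the start of the Visit 6 bronchoscopy, beside the planned on-treatment and non-procedural/non-LPS tables. The start of bronchoscopy is a better cut than LPS instillation: SAP 7.9.1 already lists it, and SAP 5.2.2 refers to BAL taken before the challenge, so procedural reactions can precede instillation. State how subjects without that bronchoscopy are counted.
3. Leave the on-treatment definition unchanged for the TEAE endpoint and the drug-related tables.

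No new data or visits are needed, since AEs are already collected to end of trial. The cost is SAP wording and one extra table, and LPS and procedural counts may be slightly higher.

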7.8.2 Laboratory data

The analyses of laboratory data will be descriptive in nature and will be based on BI standards (10). If possible, analyses will be based on original values. If multiple reference ranges apply for a parameter (e.g. due to different age groups), analyses will be based on normalised values, which means transforming to a standard unit and a standard reference range.

Descriptive statistics of laboratory values over time and for the difference from baseline (see Section 6.7, for on-treatment measurements) will be provided. Frequency tables of changes between baseline and last value on treatment with respect to the reference range will be presented.

CTP: *Values outside the reference range as well as values defined as clinically relevant will be highlighted in the listings.*

Urine dipstick data will neither be listed nor analysed.

Clinically relevant abnormal findings in laboratory data as judged by investigator will be reported as AEs (CTP Section 5.3.3) and will be analysed as part of AE analysis. Standard or project-specific rules for flagging clinically significant values will not be applied in this study.

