7.8.1 Adverse events

AEs will be coded with the most recent version of MedDRA.

The analyses of AEs will be descriptive in nature. All analyses of AEs will be based on the number of subjects with AEs and not on the number of AEs.

For analysis, multiple AE occurrence data on the eCRF will be collapsed into one event provided that all of the following applies:

- All AE attributes are identical (lower level term, intensity, action taken, therapy required, seriousness, reason for seriousness, relationship, outcome, AESI)
- The occurrences were time-overlapping or time-adjacent (time-adjacency of 2 occurrences is given if the later occurrence started at most 1 hour after the first occurrence ended).

For further details on summarization of AE data, please refer to 'Handling and summarization of AE data for clinical trial reports and integrated summaries' (8) [001-MCG-156] and "Handling of missing and incomplete AE dates" (4) [001-MCG-156_RD-01].

The analysis of AEs will be based on the concept of TEAEs. That means that all AEs will be assigned to the treatment, post-treatment, screening or post-study phases as defined in [Section 6.1](#).

An overall summary of AEs will be presented. This overall summary will comprise summary statistics for the class of other significant AEs according to ICH E3 and for the class of AESIs.

CTP: *The following are considered as AESIs:*

Hepatic injury

A hepatic injury is defined by the following alterations of hepatic laboratory parameters:

- *an elevation of AST and/or ALT > 3 fold upper limit normal (ULN) combined with an elevation of total bilirubin > 2 fold ULN measured in the same blood draw sample, and/or*
- *marked peak aminotransferase (ALT and/or AST) elevations ≥ 10 fold ULN*

The investigator had to classify in the eCRF whether an observed AE was an AESI or not.

According to ICH E3 (9), AEs classified as ‘other significant’ need to be reported and will include those non-serious and non-significant AEs with

- (i) ‘action taken = discontinuation’ or ‘action taken = reduced’, or
- (ii) marked haematological and other lab abnormalities or AEs which lead to significant concomitant therapy as identified by the Clinical Monitor/Investigator at the BRPM.

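### The only categorical laboratory table uses one post-challenge value per subject, so transient pre-challenge abnormalities are not counted and the size of persistent ones is lost

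*SAP*

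**What the plan says.** SAP 7.8.2 plans three laboratory outputs:

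- By-visit summaries: "Descriptive statistics of laboratory values over time and for the difference from baseline". SAP section 7 adds that the standard statistics include the minimum and maximum.
- A shift table: "Frequency tables of changes between baseline and last value on treatment with respect to the reference range will be presented".
- Listings, in which "Values outside the reference range as well as values defined as clinically relevant will be highlighted in the listings".

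The section then routes clinical relevance through adverse event (AE) reporting, "Clinically relevant abnormal findings in laboratory data as judged by investigator will be reported as AEs", and closes with "Standard or project-specific rules for flagging clinically significant values will not be applied in this study".

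SAP 7.8.1 defines a class of other significant AEs following ICH E3. One limb of it is "marked haematological and other lab abnormalities or AEs which lead to significant concomitant therapy as identified by the Clinical Monitor/Investigator at the BRPM". No numerical criterion for *marked* is given. SAP 6.2 combines that blinded report planning meeting (BRPM) with the database lock meeting.

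**The concern.** Without a flagging rule, the categorical summary depends on the shift table, and that table has two limits. It takes one value per subject, the last on treatment, and it recognises only in or out of range. A value just beyond the limit and one many times the limit share a cell.

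The choice of the last value matters in this design because every subject has an endotoxin challenge and bronchoscopy at Visit 6. A laboratory effect of the drug alone is best seen at Visits 4 and 6, before the challenge. If those values are not the ones tabulated, the arms cannot be compared from any table on how many subjects developed an abnormality on drug alone. Safety is named in the trial's title, and protocol 7.7 calls this the first trial in healthy smokers with 28-day exposure.

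**Working it through.** The SAP gives no figure to reproduce. The check is which draw feeds the shift table, and which output would show a given abnormality.

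**Inputs**

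- Safety blood draws: Visits 1, 2, 4, 6, 7 and 8 (protocol flow chart; 6.2.2 and 6.2.3).
- Baseline: last value before first intake at Visit 2 (SAP 6.7).
- Visit 6 procedures come before the bronchoscopy (protocol 6.2.4), so I take the Visit 6 draw as pre-challenge.
- Last dose: evening of Day 28, ideally close to 22:00 (protocol 4.1 and 6.2.4).
- On-treatment phase ends 4 days after the last dose (SAP 6.1).
- Visit 7 is Day 29; Visit 8 is Day 32 to 34 (flow chart).

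**Which draw is the last on treatment**

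End of phase = Day 28, about 22:00, + 4 × 24 h = Day 32, about 22:00.

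- Visit 8 on Day 32: inside. There are four on-treatment draws (Visits 4, 6, 7, 8) and the table uses Visit 8.
- Visit 8 on Day 33 or 34: outside. There are three on-treatment draws (Visits 4, 6, 7) and the table uses Visit 7.

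Visit 6 may move by 2 days either way. Assuming that the last dose falls on the evening of Visit 6 and Visit 8 keeps its calendar slot, the phase ends between Day 26 + 4 = Day 30 (Visit 8 always outside) and Day 30 + 4 = Day 34 (Visit 8 normally inside). In each case the tabulated value of a completer is from Visit 7 or 8, after the challenge. Visits 4 and 6 supply it only for subjects who lack a later on-treatment draw.

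The table thus uses 1 of 3 or 1 of 4 on-treatment draws. Both pre-challenge draws are among those unused.

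**Where an abnormality appears (completer, in range at baseline)**

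| Value | Shift table | By-visit statistics | Listing | AE tables |
|---|---|---|---|---|
| Marked at Visit 4 or 6, in range at last draw | Counted as in range | Only if it is the visit minimum or maximum | Shown, highlighted | Only if reported as an AE |
| Marked and still present at last draw | Out of range, degree lost | As above | Shown, highlighted | Only if reported as an AE |
| Slightly out of range at last draw | Out of range, same cell as the row above | As above | Shown, highlighted | Only if reported as an AE |

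**What *marked* adds**

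The class in SAP 7.8.1 contains AEs only: "AEs classified as ‘other significant’ need to be reported and will include those non-serious and non-significant AEs with" the listed features. Its laboratory limb cannot bring in a value that nobody reported as an AE. What it lacks is a stated basis for calling a reported abnormality marked.

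**The case against.** Much of the case for leaving the plan alone stands.

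- A reader might infer that every laboratory rule has been switched off. That is not so. Values outside the reference range are still highlighted, and numerical hepatic-injury criteria remain in SAP 7.8.1, although a case enters that table only when the investigator classifies an AE as such.
- A reader might infer that marked abnormalities are counted in no table at all. An abnormality present at the last on-treatment value is counted as out of range whether or not it is an AE.
- A reader might see a contradiction between "Standard or project-specific rules for flagging clinically significant values will not be applied in this study" and the promise that "values defined as clinically relevant will be highlighted in the listings", or an undeclared change that SAP section 4 should have listed. Neither is supported. The two sentences fit together if clinical relevance means the investigator's judgement, and the visible protocol promises no automatic flagging.
- The judgement on *marked* is made at a blinded meeting, and protocol 4.1.5.1 keeps the blind until after database lock, so it cannot be steered by arm.
- Individual values of all subjects are listed by treatment group, subject and visit. With about 25 per arm, a patient reader could make the count by hand.
- Safety analysis is descriptive, and a table would add little formal power. With 25 per arm, 5 versus 0 gives a two-sided Fisher p of 0.0502, so 6 versus 0 is needed for p < 0.05. At true rates of 10% and 0% that happens about 3% of the time.

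The listing argument shows that the information exists, not that the plan summarises it. The power argument is right, but the purpose here is description: a count made by the same rule for every subject and visit, which the last-value table does not give.

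**Conclusion.** The point holds as a gap in the displays. The one categorical laboratory table takes, for completers, a value drawn after the challenge. It leaves out two of three or three of four on-treatment draws, including both pre-challenge draws, and it discards degree. Both arms are challenged, so the randomised comparison remains fair. However, the tabulated value mixes any effect of the drug alone with the response to challenge and bronchoscopy, which the drug is intended to modify. The SAP already separates procedural, endotoxin-related and other on-treatment AEs; the laboratory table has no matching separation.

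The practical harm cannot be quantified, because it depends on how many abnormalities are transient and go unreported as AEs. The improvement is worth making because it uses data already collected.

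The conclusion rests on dosing and visits on schedule, and on the visible text. The sponsor's laboratory standard (SAP reference 10) is not available and part of the protocol's laboratory section is missing, so a further table or definition there cannot be excluded. A definition held only in the standard flagging rules would not help, since the SAP says those rules are not applied.

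**What to change.** Amend SAP 7.8.2 before unblinding:

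1. Add a table by arm and parameter of subjects with a newly occurring out-of-range value at any on-treatment visit, taking the worst value against baseline. The denominator is subjects with at least one value in the period shown.
2. Show the pre-challenge visits (4 and 6) separately from the post-challenge visits (7, and 8 only when within 4 days of the last dose).
3. Replace the sentence that disapplies the flagging rules: apply the sponsor's existing standard rules to the same values and count flagged subjects by arm. No new threshold is proposed. The sponsor should confirm that the rules suit this trial, since their content cannot be checked here.
4. Give the blinded list of flagged values to the BRPM as the basis for *marked* in SAP 7.8.1.
5. State that *clinically relevant* in the listings means the investigator's judgement.

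Keep the last-value shift table. The cost is one or two more standard tables and a few SAP sentences, with no new data collection. The downside is that some flagged values will be clinically trivial and need a line of comment.
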